7.1 WU PI Reporting Requirements

7.1.1 Reporting to the Human Research Protection Office (HRPO) at Washington University

Reporting will be conducted in accordance with Washington University IRB Policies.

Pre-approval of all protocol exceptions must be obtained prior to implementing the change.

7.1.2 Reporting to the Quality Assurance and Safety Monitoring Committee (QASMC) at Washington University

The PI is required to notify the QASMC of any unanticipated problems involving risks to participants or others occurring at WU or any BJH or SLCH institution that has been reported to and acknowledged by HRPO. (Unanticipated problems reported to HRPO and withdrawn during the review process need not be reported to QASMC.)

QASMC must be notified within **10 days** of receipt of IRB acknowledgment via email to [contact]. Submission to QASMC must include the myIRB form and any supporting documentation sent with the form.

7.2 Exceptions to Expedited Reporting

Events that do not require expedited reporting as described in Section 7.1 include:

- planned hospitalizations
- hospitalizations < 24 hours
- respite care
- events related to disease progression

Events that do not require expedited reporting must still be captured in the EDC.

8.0 CORRELATIVE STUDIES

8.1 Blood Sample Collection and Processing

Patients will be have up to 50 mL of anticoagulated blood collected in up to 5 EDTA purple top tubes at the following time points:

- Baseline
- immediately after radiotherapy completion (Fraction 5)
- 14 days after radiotherapy
- 30-days follow-up

All samples will be marked with the patient's study number, initials, and date of sampling with the use of an indelible marker.

Blood and tissue samples will be stored in [name] lab in the Cancer Biology Division of the Department of Radiation Oncology.

8.1.1 Plasma and Whole Blood

Each sample will be labeled with a unique de-identified specimen ID number, and stored in [name] lab until analysis. Specifically, blood samples (up to 50 mL) will be collected in 5 EDTA (10 mL each) purple top tubes at baseline, post-

treatment (i.e. immediately following fraction 5), 14 days after treatment, and at 30 days follow-up. EDTA whole blood samples will be spun at 1200 g and processed for platelet depleted plasma and peripheral white blood cells. Nucleated white blood cells will be isolated using Ficoll or Lymphoprep extraction using Sepmate tubes, washed in phosphate buffered saline, then divided into approximately 10×10^6 cells/aliquot, and cryopreserved at -80°C for 24-72 hours, then moved for longer term storage in a LN₂ tank. All plasma and aliquots of platelet-depleted whole blood will also be stored at -80°C .

All samples should be sent to:

[name]., Ph.D.
[name]. (Lab Manager)
[name]
[contact], [contact] (cell)

9.0 DATA SUBMISSION SCHEDULE

Case report forms with appropriate source documentation will be completed according to the schedule listed in this section.

| Case Report Form | Submission Schedule |
|---------------------------------------|---|
| Original Consent Form | Prior to registration |
| On-Study Form Medical History Form | Prior to starting treatment |
| Specimen Collection Form | Screening, immediately after radiotherapy completion (Fraction 5), 14 days after radiotherapy, and 30 days after radiotherapy |
| Questionnaires | Baseline, after radiation at 2 weeks, 1 month, and 3 months |
| Toxicity Form | Continuous |
| Treatment Summary Form | Completion of treatment |
| Follow Up Form | After radiation at 2 weeks, 1 month, and 3 months |
| Death Form | At time of death (if applicable) |

9.1 Adverse Event Collection in the Case Report Forms

All adverse events that occur beginning with start of treatment (minus exceptions defined in Section 7.0) must be captured in the Toxicity Form. Baseline AEs should be captured on the Medical History Form.

Participant death due to disease progression should be reported on the Toxicity Form as grade 5 disease progression. If death is due to an AE (e.g. cardiac disorders: cardiac arrest), report as a grade 5 event under that AE. Participant death must also be recorded on the Death Form.

10.0 DATA AND SAFETY MONITORING

In compliance with the Washington University Institutional Data and Safety Monitoring Plan, the Principal Investigator will provide a Data and Safety Monitoring (DSM) report to the Washington University Quality Assurance and Safety Monitoring Committee (QASMC) semi-annually beginning six months after accrual has opened (if at least one patient has been enrolled) or one year after accrual has opened (if no patients have been enrolled at the six-month mark).

The Principal Investigator will review all patient data at least every six months, and provide a semi-annual report to the QASMC. This report will include:

- HRPO protocol number, protocol title, Principal Investigator name, data coordinator name, regulatory coordinator name, and statistician
- Date of initial HRPO approval, date of most recent consent HRPO approval/revision, date of HRPO expiration, date of most recent QA audit, study status, and phase of study
- History of study including summary of substantive amendments; summary of accrual suspensions including start/stop dates and reason; and summary of protocol exceptions, error, or breach of confidentiality including start/stop dates and reason
- Study-wide target accrual
- Protocol activation date
- Average rate of accrual observed in year 1, year 2, and subsequent years
- Expected accrual end date
- Objectives of protocol with supporting data and list the number of participants who have met each objective
- Measures of efficacy (phase I studies only if efficacy is objective of the protocol)
- Measures of efficacy
- Early stopping rules with supporting data and list the number of participants who have met the early stopping rules
- Summary of toxicities
- Abstract submissions/publications
- Summary of any recent literature that may affect the safety or ethics of the study

The study principal investigator and Research Patient Coordinator will monitor for serious toxicities on an ongoing basis. Once the principal investigator or Research Patient Coordinator becomes aware of an adverse event, the AE will be reported to the HRPO and QASMC according to institutional guidelines.

11.0 STATISTICAL CONSIDERATIONS

11.1 Study Design

This is a single arm study where 20 eligible patients with non-hematologic malignancies patients with large tumors (≥ 4.5 cm) will undergo radiotherapy using Lattice SBRT. Lattice SBRT will be prescribed to 20 Gy in 5 fractions delivered every other day with a LATTICE simultaneous integrated boost (SIB) to 66.7 Gy in 5 fractions. Patients will be

followed for 90 days after the completion of all therapy for treatment-related toxicity assessment. An exploratory study will analyze blood-based markers of treatment response, so blood will be drawn prior to and after completion of radiotherapy.

11.2 Study Endpoints

The primary endpoint is treatment related severe adverse event rate defined as the percentage of patients with grade 3 or higher non-hematological toxicities as scored by NCI Common Terminology Criteria for Adverse Events (CTCAE) version 5.

The exploratory endpoints include blood-based markers of treatment response, pain response to Lattice SBRT, patient reported quality of life (QoL) outcomes using the in-field response, PROMIS Global, Physical Function, Pain Interference, Anxiety, and Depression questionnaire, before and after treatment with Lattice SBRT.

11.3 Data Analysis

Demographic and clinical characteristics will be summarized using descriptive statistics. Paired t-test and/or paired-sample Wilcoxon Signed Rank test will be used to compare the QoL scores between before and after treatment with Lattice SBRT.

11.4 Power Analysis and Sample Size

Approximately 20 evaluable patients will be enrolled. The proposed sample size was chosen to allow assessment of safety. With an expected \geq grade 3 non-hematological toxicity rate around 30%, there is a 99.53% probability of observing at least one toxicities in the 20 patients.

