| 10.0 DATA AND SAFETY MONITORING..... | 28 |
| 11.0 STATISTICAL CONSIDERATIONS..... | 28 |

[figure not shown]
| | | |
|------|---|----|
| 11.1 | Study Design | 28 |
| 11.2 | Study Endpoints | 29 |
| 11.3 | Data Analysis | 29 |
| 11.4 | Power Analysis and Sample Size | 29 |
| 11.5 | Accrual | 29 |
| 11.6 | Continuous Toxicity Monitoring using Pocock-type boundary | 29 |
| 12.0 | REFERENCES | 31 |
| | APPENDIX A: ECOG Performance Status Scale | 35 |
| | APPENDIX B: Definitions for Adverse Event Reporting | 36 |
| | APPENDIX C: Reporting Timelines | 38 |
| | APPENDIX D: PRO-CTCAE Inventories | 40 |

PROTOCOL SUMMARY

Synopsis

| | |
|---|---|
| Title: | A Trial of Palliative Lattice Stereotactic Body Radiotherapy (SBRT) |
| Study Description: | Lattice SBRT will be used to deliver palliative radiotherapy to large (≥ 4.5 cm) tumors. The safety and efficacy of this approach will be assessed for this novel treatment technique. |
| Objectives: | 
Primary Objective: To evaluate the safety of 5-fraction palliative Lattice SBRT in patients with non-hematologic malignancies with large lesions who are planning to undergo palliative radiotherapy (≥ 4.5 cm).
 
Exploratory Objectives:
 
 1. To assess pain response to Lattice SBRT 2. To assess patient-reported toxicity outcomes 3. To assess patient reported quality of life outcomes 4. To evaluate blood for immune- and tumor damage-associated response with Lattice SBRT |
| Endpoints: | 
Primary: Rate treatment-related, non-hematologic CTCAE version 5.0 \geq Grade 3 toxicity
 
Exploratory: Pain assessment, PROMIS Global, Physical Function, Pain Interference, Anxiety, and Depression, peripheral blood immune-related biomarkers.
 |
| Study Population: | Ten patients will be enrolled, all ≥ 18 years of age with ECOG ≤ 2 . All genders and races will be included. |
| Phase: | Unphased |
| Description of Sites / Facilities Enrolling: | This is a single-institutional study |
| Description of Study Intervention: | 5-fraction Lattice SBRT delivered to 20 Gy with a simultaneous integrated boost (SIB) to 66.7 Gy. |
| Study Duration: | 6 months plus 2 weeks for treatment and 90 days follow up |
| Participant Duration: | 2 weeks of treatment plus 90 days follow up. |

SCHEMA

SCHEDULE OF ACTIVITIES

| | Screening | Pre-Tx / Baseline | Fx 1 | Fx 2 | Fx 3 | Fx 4 | Fx 5 | EOT (2 weeks post) ⁵ | 30 Day F/U ⁶ | 90 Day F/U ⁶ |

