4.5 Strategies for Recruitment and Retention

Our institution sees a high volume of patients that are referred for palliative radiotherapy.

The primary source of patients who are eligible for this study will be radiation oncologists within our department. The most likely service lines to see patients with large tumors in need of palliative radiotherapy are sarcoma, thorax (i.e. lung cancer), gastrointestinal, gynecologic, palliative, and head and neck. [name] (service line chief of sarcoma) is the PI, and the other service line chiefs are enthusiastic about this trial and are listed as co-investigators: [name] (Thorax), [name] (Gastrointestinal), [name] (Gynecologic), [name] (Palliative), and [name] (Head and Neck). Additionally, a full-time research coordinator will be assigned to this study who will be screening all patients who are referred to our department for palliative radiotherapy.

With the current rate of patients in need of palliative radiotherapy presenting to our department, we anticipate approximately 125 patients per year will be eligible for this protocol. A conservative estimate is that 20% of these patients will consent to participate in this study. This yields an estimated accrual of 25 patients per year. We anticipate that we will enroll 10 patients of all genders, races, and ethnicities. Given the hypofractionated course of therapy, 90% of patients should be able to complete therapy. We anticipate that we will accrue approximately 1-2 patients per month, therefore completing accrual in 6 months. Patients will be accrued from the outpatient clinics and inpatient hospitals of one U.S. site. Potential participants will be identified by our multidisciplinary team physicians and discussed in tumor board.

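### The protocol gives two enrolment targets, 10 and 20, and the figures supporting its safety design were calculated for neither; they fit 15

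*Combined protocol and SAP*

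**What the plan says.** **Target of 10.** The Synopsis states "Ten patients will be enrolled" and gives the study duration as "6 months plus 2 weeks for treatment and 90 days follow up". Section 4.5 agrees: "We anticipate that we will enroll 10 patients of all genders, races, and ethnicities". On pace, 4.5 says "This yields an estimated accrual of 25 patients per year" and then "We anticipate that we will accrue approximately 1-2 patients per month, therefore completing accrual in 6 months".

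**Target of 20.** Section 11.1 opens with "This is a single arm study where 20 eligible patients". Section 11.4 says "Approximately 20 evaluable patients will be enrolled" and, for an expected toxicity rate of about 30%, that "there is a 99.53% probability of observing at least one toxicities in the 20 patients". Section 11.5 expects about one patient per month and 20 patients in 10 to 12 months.

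**Stopping rule.** Section 11.6 halts accrual when the number of events reaches b_n among n patients with full follow-up, and refers to a table for b_n. The table's columns run from n = 4 to n = 15. The sentence after the table restates the rule as 4 of 4, 6 of 8, 7 of 11 and 9 of 20. The operating characteristics that follow give, at a 30% rate, a stopping probability of 0.0447 and expected enrolment of 14.71; at 40% they give 0.1707 and 13.96.

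**The concern.** Safety is the only primary objective, and Section 1.6.2 describes the technique as untested. How many patients receive it, and when accrual halts, are basic design facts. The first differs twofold between sections. The second has no table boundary after patient 15 if enrolment goes to 20.

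Section 10.0 requires target accrual and the status of the stopping rule to be reported to the monitoring committee. With two targets and two versions of the rule, neither can be reported unambiguously. The committee would also be relying on operating characteristics that, taken as a set, belong to neither stated design.

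The precision of the primary result changes too. If 30% of patients have an event, the exact (Clopper–Pearson) 95% interval is 6.7% to 65.2% for 3 of 10 and 11.9% to 54.3% for 6 of 20. The plan sets no precision target, so these intervals show what the choice of N changes; they do not show a failed criterion.

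**Working it through.** **Inputs.** Event rate 0.30 (11.4, 11.6) and undesirable rate 0.40 (11.6); candidate N of 10 (Synopsis, 4.5) and 20 (11.1, 11.4, 11.5); the boundary table, the rule in words and the operating characteristics (11.6).

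**1. The probability in 11.4.** P(at least one event) = 1 − 0.7^n.

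| n | 1 − 0.7^n |
|---|---|
| 10 | 97.18% |
| 15 | 99.53% |
| 20 | 99.92% |

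The printed 99.53% is the value for 15.

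**2. Expected enrolment, without using the boundary values.** The first look in the table is at patient 4, so a trial that stops has enrolled at least 4 patients and one that does not stop enrols N. With N = 20 and the printed stopping probabilities, E[N] ≥ 20 − 16 × P(stop):

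- 30% rate: 20 − 16 × 0.0447 = 19.28; printed 14.71.
- 40% rate: 20 − 16 × 0.1707 = 17.27; printed 13.96.

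The printed values are therefore impossible with a maximum of 20. Both exceed 10, so a maximum of 10 is impossible too.

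**3. Reproducing the 11.6 table.** This is an exact binomial recursion over patients and events, stopping when events ≥ b_n. The boundary row as it reads in the available text has 11 values for 12 patient counts. Aligned to n = 4–14, it gives stopping 0.028 and E[N] 14.79 at a 30% rate with a maximum of 15; aligned to n = 5–15, it gives 0.061 and 14.53. Neither matches. One value was then inserted in each of the 10 distinct ways that keep the row non-decreasing, with maxima of 15 and 20. Only b = 4, 5, 5, 6, 6, 6, 7, 7, 8, 8, 9, 9 for n = 4–15, with a maximum of 15, reproduces all eight printed rows. It also contains the 4 of 4, 6 of 8 and 7 of 11 given in the text.

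The same boundary under each maximum:

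| Maximum | P(stop), 30% / 40% | E[N], 30% / 40% | Expected events, 30% / 40% |
|---|---|---|---|
| Printed | 0.0447 / 0.1707 | 14.71 / 13.96 | 4.41 / 5.58 |
| 15 | 0.0447 / 0.1707 | 14.71 / 13.96 | 4.41 / 5.58 |
| 20 | 0.0447 / 0.1707 | 19.49 / 18.11 | 5.85 / 7.24 |
| 10 | 0.032 / 0.113 | 9.90 / 9.66 | 2.97 / 3.87 |

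**4. Adding the 9-of-20 look.** With the same boundary to n = 15 plus a look at 9 of 20, P(cross) is 0.126 at 30% and 0.421 at 40%. If the look is taken only once all 20 have completed, E[N] stays at 19.49 and 18.11. If a ninth event at any time from patient 16 halts accrual, E[N] is 19.38 and 17.70. The printed properties do not include this look.

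**5. Accrual.** Twenty patients take 20 months at one per month (the 11.5 rate), 10 months at two per month (the top of the 4.5 range), and 20/25 × 12 = 9.6 months at 25 per year (4.5). So the 10 to 12 months in 11.5 does not follow from its own rate. Ten patients take 5 to 10 months at one to two per month; the six months in the Synopsis and 4.5 is stated for 10.

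**The case against.** The 11.4 error is 0.39 percentage points, is conservative if N is 20, and drives no decision. The table's stopping probabilities are unchanged at 20, because no boundary applies after patient 15; only the descriptive columns move. A look at 9 of 20 taken after everyone has completed saves little or no accrual. The match to 15 in 11.6 depends on a boundary cell that had to be inferred, and that cell may have been lost when the PDF was converted. Twenty patients in 10 to 12 months is also compatible with the upper part of the 4.5 accrual range.

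All of this is correct, and it sets the weight of the parts. The arithmetic mismatches alone would be minor, and the short boundary row is not counted against the plan. But none of it explains 10 against 20. Neither number is described as a stage, a cohort or an evaluable subset. Dropout does not account for the gap: 4.5 expects 90% to complete therapy, and 5.6 makes anyone who receives one fraction evaluable for toxicity. The lower bound on expected enrolment excludes 20 without using the damaged row. The difference between the table and the rule in words is also unaffected.

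**Conclusion.** The concern holds and should be corrected before the plan is relied on. The enrolment target is contradictory (10 against 20). The rule in the table and the rule in words differ after patient 15. The probability in 11.4 and the operating characteristics in 11.6, as a set, describe neither target.

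The largest numerical consequence is in the stopping rule. At the 40% rate the plan calls undesirable, the probability of crossing is 0.171 under the table and 0.421 with the look in the text, about 2.5 times as high. Expected enrolment at a 30% rate is 14.71 as printed, against 19.49 with a maximum of 20.

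That the printed figures fit neither 10 nor 20 rests only on the printed values and the first look at patient 4. That they were computed for 15 is an inference: 11.4 supports it directly, and 11.6 supports it if the boundary at patient 9 is 6. The figures with the 9-of-20 look use the same reconstructed row.

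**What to change.** - State one N in the Synopsis, 4.5 and 11.1 to 11.6. The choice is the sponsor's.
- Restate the 11.4 probability for that N: 97.18% at 10, 99.53% at 15, 99.92% at 20.
- Reconcile the 11.6 table and text into one rule that covers every patient up to N, and confirm against the source file that the boundary row has a value for each patient count.
- Recompute the operating characteristics for that N and rule. If N is 15 and the source row carries 6 at patient 9, the 11.4 percentage and the printed operating characteristics stand, but every statement of 10 or 20, including the 9-of-20 look, must change.
- Make the accrual rate and duration in the Synopsis, 4.5 and 11.5 agree with N and with each other.

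The cost is protocol wording, one restated probability and a short exact binomial calculation. The correction does not itself call for more patients; whether enrolment rises depends on which N the sponsor adopts.

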11.5 Accrual

The rate of accrual for the study is expected to be about 1 patient per month. It is estimated 20 eligible patients will be enrolled in 10-12 months.

11.6 Continuous Toxicity Monitoring using Pocock-type boundary

The toxicities will be reviewed and monitored on a continuous basis. Early stopping of this trial will be based on the excessive Lattice SBRT treatment emergent severe adverse events (TEAE) of grade 3 or higher non-hematological rate. We assume the TEAE rate is expected ~30% and a toxicity rate of 40% or more is not desired. Sequential boundaries will be used to monitor dose-limiting toxicity rate after three patients are enrolled and evaluable for toxicity. The accrual will be halted if excessive numbers of TEAE are seen, that is, if the number of TEAE is equal to or exceeds b_n out of n patients with full follow-up (see table below). This is a Pocock-type stopping boundary that yields the probability of crossing the boundary at most 0.3 when the rate of TEAE is equal to the acceptable rate of 0.3 (Ivanova, Qaqish, and Schell 2005).

| | | | | | | | | | | | | |
|--------------------|---|---|---|---|---|---|----|----|----|----|----|----|
| number of patients | 4 | 5 | 6 | 7 | 8 | 9 | 10 | 11 | 12 | 13 | 14 | 15 |
|--------------------|---|---|---|---|---|---|----|----|----|----|----|----|

| | | | | | | | | | | | |
|---------------|---|---|---|---|---|---|---|---|---|---|---|
| Boundary (bn) | 4 | 5 | 5 | 6 | 6 | 7 | 7 | 8 | 8 | 9 | 9 |
|---------------|---|---|---|---|---|---|---|---|---|---|---|

Thus, based on the continuous monitoring algorithm for toxicity using Pocock-type boundary, the study will halt if excessive Lattice SBRT -related adverse events occur in the 4 of the first 4 patients, or 6 of the first 8, or 7 of the first 11, or 9 of the 20 patients has completed the trial.

The operating characteristics including early stopping probability, expected number of TEAEs and associated with the calculated boundaries are listed below.

| TEAE rate | Early stopping (hitting the boundary) probability | Expected number of TEAEs | Standard deviation on number of TEAEs | Expected number of patients enrolled | Standard deviation of number of patients enrolled | Expected TEAE rate | Standard deviation on TEAE rate |
|------------------|--|---------------------------------|--|---|--|---------------------------|--|
| 0.30 | 0.0447 | 4.41 | 1.65 | 14.71 | 1.50 | 0.31 | 0.15 |
| 0.40 | 0.1707 | 5.58 | 1.54 | 13.96 | 2.65 | 0.43 | 0.18 |
| 0.50 | 0.4101 | 6.24 | 1.38 | 12.49 | 3.67 | 0.55 | 0.19 |
| 0.60 | 0.6957 | 6.24 | 1.40 | 10.40 | 4.06 | 0.67 | 0.18 |
| 0.70 | 0.9052 | 5.72 | 1.38 | 8.18 | 3.61 | 0.77 | 0.16 |
| 0.80 | 0.9878 | 5.05 | 1.11 | 6.31 | 2.60 | 0.85 | 0.14 |
| 0.90 | 0.9998 | 4.46 | 0.72 | 4.96 | 1.53 | 0.93 | 0.10 |
| 1.00 | 1.0000 | 4.00 | 0.00 | 4.00 | 0.00 | 1.00 | 0.00 |

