5.6 Definitions of Evaluability

All patients enrolled on the study are evaluable for toxicity if they have received at least one fraction of radiation. Patients are evaluated from first receiving study treatment until 90 days after the conclusion of treatment or death.

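### Section 11.6 leaves unclear whether a toxicity counts toward the stopping boundary once it is known or only after the patient's full follow-up of about 104 days

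*Combined protocol and SAP*

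**What the plan says.** Section 11.6 opens by stating that "The toxicities will be reviewed and monitored on a continuous basis". It then says "Sequential boundaries will be used to monitor dose-limiting toxicity rate after three patients are enrolled and evaluable for toxicity". Section 5.6 makes a patient evaluable for toxicity after a single fraction.

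The sentence that halts accrual compares the number of TEAEs with b_n "out of n patients with full follow-up (see table below". A later sentence, opening with the word Thus, restates the rule without repeating that condition: "the study will halt if excessive Lattice SBRT -related adverse events occur in the 4 of the first 4 patients". Three more limits follow in the same sentence, for 8, 11 and 20 patients. The first three of its four limits carry no follow-up condition; the last one, at 20 patients, refers to completion.

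On the rates, section 11.6 says: "We assume the TEAE rate is expected ~30% and a toxicity rate of 40% or more is not desired". Its operating-characteristics table includes a column headed "Expected number of patients enrolled".

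The synopsis gives participant duration as 2 weeks of treatment plus 90 days. Toxicity visits fall at 14, 30 and 90 days after radiotherapy (5.1, 5.10.1). Section 11.5 expects about 1 patient per month, but also 20 patients in 10 to 12 months. Section 4.5 expects 1 to 2 per month and 10 patients in 6 months. Neither accrual section, nor 11.6 itself, pauses enrolment while follow-up matures.

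**The concern.** A monitor who learns of a grade 3 event at the day-14 visit cannot tell from 11.6 whether it counts now or only once that patient has passed day 90. This is the plan's only numerical stopping rule for the primary safety endpoint, and section 1.6.2 says the technique has not been tested. Under the literal reading accrual continues while the count waits, so a halt comes later than one based on events as they become known. The delay costs most when toxicity is unexpectedly high, which is the case the rule exists for.

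Section 11.6 also labels the monitored event in three ways (treatment-emergent, dose-limiting, Lattice SBRT-related) and counts it once as events and once as patients. Section 11.2 defines the endpoint per patient and as treatment-related.

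**Working it through.** **1. Reproducing the table.** The boundary row shows 11 values for 12 sample sizes, possibly a text-extraction loss. Taking b_n = 4,5,5,6,6,6,7,7,8,8,9,9 for n = 4 to 15 agrees with the restated limits (b_4 = 4, b_8 = 6, b_11 = 7). An exact binomial recursion, with a 15-patient maximum and each outcome known before the next patient enters, gives:

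| TEAE rate | Stopping probability | Expected enrolled | Expected TEAEs |
|---|---|---|---|
| 0.30 | 0.0447 | 14.71 | 4.41 |
| 0.40 | 0.1707 | 13.96 | 5.58 |
| 0.50 | 0.4101 | 12.49 | 6.24 |
| 0.70 | 0.9052 | 8.18 | 5.72 |
| 1.00 | 1.0000 | 4.00 | 4.00 |

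These match the plan. The last row (exactly 4.00 enrolled, SD 0) shows the zero-lag assumption directly.

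**2. The lag.** 14 + 90 = 104 days, or 104/30.44 = 3.42 months. The rates are 1 per month (11.5), 1.67 (20 in 12 months, or 10 in 6) and 2 (20 in 10 months). If patient k enrols at (k − 1)/rate months, the number enrolled when patient n completes follow-up is n + floor(3.42 × rate), capped at N. The floor term is 3, 5 or 6, so the first look (n = 4) comes with 7, 9 or 10 patients enrolled.

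**3. What the lag changes in the table.** The count among the first n patients can only rise, and it ends at the same value under either reading. The probability of ever crossing is therefore the same. The enrolled column does change. For N = 20 with looks to n = 15, the larger maximum alone adds 5 × (1 − stopping probability):

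- 30%: 14.71 + 5 × 0.9553 = 19.49; with the lag, 19.6 to 19.8.
- 50%: 12.49 + 5 × 0.5899 = 15.44; with the lag, 16.7 to 17.9.
- 70%: 8.18 + 5 × 0.0948 = 8.65; with the lag, 11.4 to 14.1.

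The 15-patient maximum explains most of the gap at 30% and 50%. At 70% the lag does.

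**4. Full follow-up against events counted when known.** The documents give no onset data, so three patterns are assumed: early (uniform over days 7 to 60), visit-based (known only at the 14-, 30- or 90-day visit, one third each) and late (uniform over days 60 to 104). Full-follow-up figures are exact; the others are simulated, 200,000 runs per setting. Each cell gives values at 1/1.67/2 patients per month.

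Mean enrolled, N = 20, looks to n = 15:

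| Rate | Full follow-up | Early | Visit-based | Late |
|---|---|---|---|---|
| 30% | 19.6/19.7/19.8 | 19.5/19.6/19.6 | 19.6/19.6/19.7 | not tabulated |
| 40% | 18.6/19.0/19.1 | 18.2/18.4/18.4 | 18.4/18.7/18.8 | 18.5/18.8/19.0 |
| 70% | 11.4/13.2/14.1 | 9.2/10.0/10.3 | 10.1/11.6/12.1 | 10.7/12.3/13.2 |

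The differences, taken before rounding, are 0.1 to 0.2 patient at 30%. At 40% they are 0.4 to 0.7 (early), 0.2 to 0.3 (visit-based) and about 0.1 to 0.2 (late). At 70% they are 2.2 to 3.7 (early), 1.2 to 1.9 (visit-based) and 0.7 to 0.9 (late).

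Probability of a halt before the last enrolment, N = 10:

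| Rate | Full follow-up | Early | Visit-based | Late |
|---|---|---|---|---|
| 30% | 0.02/0.01/0.00 | 0.03/0.02/0.02 | 0.02/0.01/0.01 | not tabulated |
| 40% | 0.05/0.03/0.00 | 0.09/0.07/0.06 | 0.07/0.04/0.03 | not tabulated |
| 70% | 0.44/0.24/0.00 | 0.66/0.55/0.51 | 0.55/0.36/0.27 | 0.45/0.28/0.17 |

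The 70% full-follow-up entries can be checked by hand. Crossing at n = 4 has probability 0.7^4 = 0.240. First crossing at n = 6 needs 3 of the first 4 and then both of the next two: 4 × 0.3 × 0.7^5 = 0.202. At 1 per month both come before the tenth enrolment (0.240 + 0.202 = 0.442). At 1.67 per month only n = 4 does (0.240). At 2 per month neither does: patient 4 completes follow-up at month 1.5 + 3.42 = 4.92, after patient 10 enrols at month 4.5.

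**The case against.** The strongest reply is that 11.6 states one rule, once in full and once in shorthand. The second sentence opens with Thus, uses the same thresholds and ends with patients who have completed the trial. That reading is fair. A reader might infer a flat contradiction, but the text supports only an ambiguity. It remains one because three of the four restated limits drop the follow-up condition, and because monitoring starts with evaluable patients, who need only one fraction.

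A reader might also infer that the operating-characteristics table is wrong for the literal rule. Its main column is not: the stopping probability does not depend on the lag.

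Nor do the documents support the idea that early deaths fall outside the count. Section 5.6 says "Patients are evaluated from first receiving study treatment until 90 days after the conclusion of treatment or death", so a patient who dies has a complete evaluation period.

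A reader might conclude that the rule can never stop accrual. That holds only for 10 patients at 2 per month. The pace in 4.5 (10 in 6 months, 1.67 per month) leaves a small window.

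Finally, safety review does not stop in the meantime. Toxicity Forms are submitted continuously (9.0) and serious toxicities are watched on an ongoing basis (10.0). This stands, but neither section sets a numerical limit.

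The small effect at the planned rates also stands, as does its dependence on assumed onset.

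**Conclusion.** The point holds as an ambiguity that is worth fixing. Following the operative sentence literally gives a later halt than counting events when known. With 20 patients the cost is at most about 0.2 extra patient at 30% and about 0.1 to 0.7 at 40%. It is material only at unexpectedly high toxicity: at 70%, about 0.7 to 0.9 patient with late onset and 2.2 to 3.7 with early onset. With 10 patients at 70%, the chance of halting before the last enrolment is lower under full follow-up, and the loss ranges from negligible (late onset, 1 per month) to 0.51 (early onset, 2 per month).

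The early-stopping column is sound for looks to n = 15. The expected-enrolled and expected-TEAE columns describe immediate outcomes and a 15-patient maximum.

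These results rest on evenly spaced accrual without a pause, a 104-day follow-up, the reconstructed boundary row, no looks after n = 15 and the assumed onset patterns. The conflict between 10, 15 and 20 patients is a separate matter.

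**What to change.** Replace the operative sentence in 11.6 with wording such as:

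> Accrual is halted as soon as, for any tabulated n, the number of patients among the first n treated who have at least one known event meeting the 11.2 endpoint (treatment-related, non-hematologic, CTCAE v5.0 grade 3 or higher) reaches b_n. A patient is counted when the event is known, without waiting for full follow-up.

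Use this one per-patient definition throughout 11.6. Label the expected-enrolled and expected-TEAE columns as assuming immediate outcomes, or recompute them for the final sample size and accrual rate.

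The cost is a protocol amendment with IRB approval. No new data stream is needed, although section 7.0 exempts some event categories from the toxicity form, so the team should confirm that every event meeting the 11.2 endpoint reaches the count. False halts at the acceptable 30% rate come slightly earlier, with a chance of at most 0.03 before the last enrolment for 10 patients. For the same looks, the eventual crossing probability is unchanged (0.0447 at 30% with looks to n = 15), and no halt comes later than under full follow-up.
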